12. STUDY SCHEDULE

Please refer to [Section 2](#), Schedule of Events for the schedule of procedures required for each visit. Note that all windows on visits should be determined relative to the date of the previous dose of ACE-536.

12.1. Screening

- Signature of the current IEC approved ICF should occur prior to initiation of any study-specific screening procedures during the 28-day screening period for all patients.
- Other than informed consent, procedures listed as part of the 28-day screening period are only applicable to patients with treatment interruption.
- ECHO or MUGA (only required for patients with treatment interruption) can be performed up to 56 days prior to C1D1. If performed as part of standard of care, ECHO/MUGA does not need to be repeated.
- Patients with treatment interruption (defined as patients who complete the EOS visit for study A536-04 and are \geq 28 days post EOS visit) will need to qualify per the additional inclusion criteria listed in [Section 9.3.2](#).
- Transfusion history will be collected from the EOS visit in study A536-04 through the C1D1 visit of A536-06 as available; TD patients will have a defined “pre-transfusion hemoglobin threshold” which will be calculated based on transfusion history and will be used for determining when to transfuse during the study. For TD patients without treatment interruption, the baseline pre-transfusion hemoglobin threshold will be the mean of all documented pre-transfusion hemoglobin values during the 12 weeks prior to C1D1 of base study A536-04 or study A536-06 (for TD patients with treatment interruption).
- Pregnancy test (urine or serum) and menstrual history is required of female patients of child bearing potential only.
- Medical history for patients with treatment interruption will include medical events occurring after EOS visit in study A536-04 and prior to C1D1 for study A536-06. Medical history for patients without treatment interruption will be taken from study A536-04.
- If at any visit the systolic blood pressure is \geq 150 mmHg, the diastolic blood pressure is \geq 95 mmHg and/or the absolute increase in either measure from baseline is \geq 20 mmHg, perform one repeat of the blood pressure assessment after a minimum of 15 minutes.
- Screen failure information will be maintained to document specific information, including but not limited to, reason for failure.

12.2. Dosing Days and Interim Visits

- Study procedures must be done prior to administration of study drug. All patients must be assessed for eligibility prior to dosing on C1D1. C1D1 MRI for LIC

(at selected sites) and EMH masses (unless site does not have feasibility to perform the assessment) and MRI of the spleen (if no prior splenectomy) can be performed up to 56 days prior to C1D1. If performed as part of standard of care, MRI for LIC, MRI for EMH and spleen do not need to be repeated. All screening and Cycle 1 Day 1 procedure results required to confirm eligibility must be obtained and reviewed prior to study drug administration in A536-06.

- On dosing days: Note that the patient dose must be calculated based on the patient's weight on the day of dosing. Starting dose level for C1D1, dose modification rules and titration rules must be reviewed and implemented prior to dosing as required per protocol (see [Sections 10.7, 10.8, 10.9](#)). If a dose delay is required per the dose modification rules (Section 10.8), the patient will not be dosed. The patient will return weekly for assessment of hematology results and AEs until the patient is eligible to receive the next dose of ACE-536 and start the next cycle. The patient should resume the study at the planned dosing cycle (e.g. if the patient missed a dose at C4D1, then they would resume dosing at C4D1 and not skip to C5D1).
- The hematology results can be collected up to 24 hours prior to the dosing day. For patients with treatment interruption, the hemoglobin should be available to confirm eligibility within one day prior to C1D1.
- Patients should be monitored for AEs throughout the study. All AEs and abnormal findings that might require modification of dosing (see [Section 10.8](#)) should be reviewed prior to dosing to ensure that the patient is still eligible to receive additional doses of ACE-536.
- Pregnancy test (urine or serum) and menstrual history is required of female patients of child bearing potential only.
- Physical exam should include an optional evaluation of gonadal size in male patients at timepoints specified in the Schedule of Events ([Section 2](#)).
- If at any visit the systolic blood pressure is ≥ 150 mmHg, the diastolic blood pressure is ≥ 95 mmHg and/or the absolute increase in either measure from baseline is ≥ 20 mmHg, perform one repeat of the blood pressure assessment after a minimum of 15 minutes.
- Patients with clinical signs of a change in spleen size or abnormality should have an abdominal ultrasound or MRI performed as needed throughout the study.
- During treatment, if the pre-transfusion hemoglobin level is increased by ≥ 1 g/dL compared to the baseline pre-transfusion hemoglobin threshold for that patient, transfusion should be delayed by a minimum of 7 days and/or the number of units transfused should be reduced by 1 or more RBC units. Patients may be transfused at the investigator's discretion for symptoms related to anemia or other requirements (e.g., infection).
- Cycles 6 through 17: Procedures and visits for Cycles 6 through 9, 10 through 13, and 14 through 17 follow the same procedures and visits as scheduled for Cycles 2 through 5, with some exceptions as noted in the Schedule of Events ([Section 2](#)).

- Cycles 24 through 87: Patients may not exceed 87 cycles or 1825 days after first dose, whichever occurs first. The last dose of ACE-536 may not be administered after Day 1825, regardless of the number of cycles completed. Procedures and visits for Cycles 24 through 27, 28 through 31, 32 through 35, 36 through 39, 40 through 43, 44 through 47, 48 through 51, 52 through 55, 56 through 59, 60 through 63, 64 through 67, 68 through 71, 72 through 75, 76 through 79, 80 through 83 and 84 through 87 follow the same procedures and visits as scheduled for Cycles 20 through 23, with some exceptions as noted in the Schedule of Events ([Section 2](#)).

12.3. End of Treatment Visit

- The EOT visit should occur 28 days (\pm 7 days) after the last dose of ACE-536.
- If at any visit the systolic blood pressure is \geq 150 mmHg, the diastolic blood pressure is \geq 95 mmHg and/or the absolute increase in either measure from baseline is \geq 20 mmHg, perform one repeat of the blood pressure assessment after a minimum of 15 minutes.
- Patients who discontinue treatment early should complete the EOT visit at the time of discontinuation.

12.4. Post-Treatment Follow-Up Visit

- The PTFU visit should occur 2 months (\pm 7 days) after the last dose of ACE-536.
- If a patient has a positive ADA result at the last visit, the patient may be asked to return for additional ADA testing every three months, until a negative result is obtained or the result is considered to be stabilized.

12.5. Long-Term Follow-Up Visits

- LTFU visits should occur beginning every 6 months (\pm 14 days) after the last dose of ACE-536 for 3 years after the last dose of ACE-536.

12.6. End of Study Visit

- The EOS visit should occur approximately 3 years after the last dose of ACE-536.
- Physical exam should include an optional evaluation of gonadal size of male patients.

12.7. Termination of Study

The sponsor may terminate this study or discontinue a cohort, after consultation with the investigator(s), or at any time, for safety or administrative reasons. The sponsor will terminate the study if the occurrence of SAEs or other findings suggests unacceptable risk to the health of the patients.

13. STUDY DRUG MATERIALS AND MANAGEMENT

13.1. Study Drug

ACE-536 is a recombinant fusion protein consisting of a modified form of the ECD of the human activin receptor IIB (ActRIIB) linked to the human IgG1 Fc domain.

13.2. Study Drug Packaging and Labeling

ACE-536 drug product will be provided as either a sterile liquid formulation or a lyophilized powder formulation for reconstitution with water. Each single-use vial of the liquid formulation contains 25 mg of ACE-536 in a 0.5 mL Tris-buffered saline solution (50 mg/mL). Each single-use vial of the lyophilic formulation may contain either 25 mg, 50 mg, or 75 mg ACE-536 for reconstitution with 0.5 mL, 1 mL, or 1.5 mL water, respectively, to form a citrate-buffered solution (50 mg/mL) for injection.

13.3. Study Drug Storage

ACE-536 liquid formulation is stored frozen at $\leq -65^{\circ}\text{C}$ until use.

ACE-536 lyophilic formulation is stored at 2-8°C until use.

13.4. Study Drug Preparation

Please refer to the Study Reference Guide, provided under separate cover, for detailed ACE-536 drug handling, administration, and storage instructions.

13.5. Study Drug Administration

ACE-536 will be administered by SC injection. Multiple injections may be required to administer the appropriate dose at higher dose levels; however, no more than 4 injections will be administered per dose.

13.6. Study Drug Accountability

Accountability for ACE-536 is the responsibility of the investigator. Investigational clinical supplies must be received by a designated person at the clinical site and kept in a secured location. The clinical site must maintain accurate records demonstrating dates and amounts of ACE-536 received, to whom it was dispensed (patient-by-patient accounting), and accounts of any ACE-536 accidentally or deliberately destroyed or returned.

Unless otherwise notified, all vials of ACE-536, both used and unused, must be saved for drug accountability purposes. The used vials may be discarded, per the institution's standard practice, after drug accountability assessment has been completed by the clinical monitor. At the end of the study, the sponsor will provide direction for the outcome of all unused vials. Following on the sponsor's instructions, the investigator must either return all unused vials of ACE-536 to the sponsor or destroy them at the clinical site. In either case, the outcome must be documented on the drug accountability log.

13.7. Study Drug Handling and Disposal

Please refer to the Study Reference Guide, provided under separate cover, for detailed ACE-536 drug product composition, drug handling, administration, storage, and disposal instructions.

14. ASSESSMENT OF SAFETY

14.1. Adverse Event Definitions

Adverse Event

An AE is any untoward medical occurrence in a patient or clinical investigation patient administered a study drug, which does not necessarily have a causal relationship with this treatment. An AE can therefore be any unfavorable and unintended sign (including an abnormal laboratory finding), symptom, or disease temporally associated with the use of the study drug whether or not it is considered related to the study drug.

Abnormal laboratory and other abnormal investigational findings (e.g. physical exam, Electrocardiogram (ECG)) should not be reported as AEs unless they are associated with clinical signs and symptoms, lead to treatment discontinuation or are otherwise considered clinically relevant by the investigator. In cases of surgical or diagnostic procedures, the condition/illness leading to such a procedure is considered as the AE rather than the procedure itself. In case of a fatality, the cause of death is considered as the AE, and the death is considered as its outcome.

Unexpected Adverse Events

An unexpected AE is an AE that is not described in nature or severity in the IB.

Events Not to Be Considered as Adverse Events

Pre-existing medical conditions/signs/symptoms present before the screening period (from study A536-04 for patients without treatment interruption; from study A536-06 for patients with treatment interruption) that do not worsen in severity or frequency during the study are defined as Baseline Medical Conditions, and are not to be considered AEs. Anticipated day-to-day fluctuations of pre-existing conditions, including the disease under study, that do not represent a clinically significant exacerbation or worsening need not be considered AEs.

Serious Adverse Event

An SAE is any AE, occurring at any dose level/regimen and regardless of causality that:

- Results in death.
- Is life-threatening: Life-threatening means that the patient was at immediate risk of death from the reaction as it occurred (i.e., it does not include a reaction which hypothetically might have caused death had it occurred in a more severe form).
- Requires inpatient hospitalization or prolongation of existing hospitalization; however, a hospitalization for an elective procedure will not be considered an SAE.
- Results in persistent or significant disability/incapacity.
- Is a congenital anomaly/birth defect.
- Is an important medical event: an important medical event is an event that may not result in death, be life-threatening, or require hospitalization but may be considered an SAE when, based upon appropriate medical judgment, it may jeopardize the patient and may require medical or surgical intervention to prevent one of the outcomes listed in the definitions for SAEs. Examples of such medical events include

allergic bronchospasm requiring intensive treatment in an emergency room or at home, blood dyscrasias or convulsions that do not result in inpatient hospitalization, or the development of drug dependency or drug abuse.

For the purposes of reporting, any suspected transmission of an infectious agent via a medicinal product is also considered a serious adverse reaction and all such cases should be reported in expedited manner.

Events Not to Be Considered as Serious Adverse Events

Elective hospitalizations to administer or to simplify study treatment or procedures are not considered SAEs.

Adverse Events of Special Interest

Events of new malignancy and premalignant lesions (excluding benign tumors or benign neoplasia) are to be reported as described in [Section 14.7](#) within 24 hours of the investigator's knowledge of the event by fax, or other appropriate method, using the SAE Report Form, and must be considered an "Important Medical Event" even if no other serious criteria apply; these events must also be documented in the appropriate page(s) of the CRF and subject's source documents. Documentation of the diagnosed malignancy must be provided at the time of reporting as a serious adverse event (e.g., any confirmatory histology or cytology results, X-rays, CT scans, etc.).

Malignancies or cancerous tumors are lesions capable of invading into adjacent tissues, and may be capable of spreading to distant tissues. A benign tumor has none of those properties.

Malignancy or cancer is characterized by anaplasia, invasiveness, and metastasis.

Premalignant or precancerous lesions refer to a state of disordered morphology of cells that is associated with an increased risk of cancer. If left untreated, these conditions may lead to cancer. Such conditions are usually either dysplasia or benign neoplasia (and the dividing line between those is sometimes blurry). Sometimes the term "precancer" is used to describe carcinoma in situ, which is a noninvasive cancer that has not progressed to an aggressive, invasive stage. Not all carcinoma in situ will progress to invasive disease.

Premalignant lesions are morphologically atypical tissue which appears abnormal under microscopic examination and in which cancer is more likely to occur than in its apparently normal counterpart.

14.2. Pregnancy and In Utero Drug Exposure

The investigator will attempt to collect pregnancy information if a female patient or a male patient's female partner becomes pregnant while the patient is participating in this study. The pregnancy information will be recorded on the appropriate form and must be submitted to the Sponsor within 2 weeks of learning of the pregnancy. The patient or partner will be followed for the outcome of the pregnancy. Information on the status of the mother and child will be forwarded to the Sponsor or designee. Generally, follow up will be no longer than 6 to 8 weeks following the estimated delivery date. Any premature termination of the pregnancy will be reported.

14.3. Severity

Investigators must evaluate the severity/intensity of AEs according to the current active minor version of the NCI-CTCAE v4.0, current minor version, preferentially using the graded scales. If there is a change in severity of an AE, it must be recorded as a separate event. If a particular AE's severity/intensity is not specifically graded, the investigator should apply the general guidelines for determination of Grade 1 through Grade 5 as listed in the NCI-CTCAE v4.0 cover page (as shown below), using their best medical judgment:

Grade 1: Mild; asymptomatic or mild symptoms; clinical or diagnostic observations only; intervention not indicated.

Grade 2: Moderate; minimal, local or noninvasive intervention indicated; limiting age-appropriate instrumental activities of daily living (preparing meals, shopping for groceries or clothes, using the telephone, managing money, etc.).

Grade 3: Severe or medically significant but not immediately life-threatening; hospitalization or prolongation of hospitalization indicated; disabling; limiting self-care activities of daily living (bathing, dressing and undressing, feeding self, using the toilet, taking medications, and not bedridden).

Grade 4: Life-threatening consequences; urgent intervention indicated.

Grade 5: Death related to AE.

14.4. Relationship to Study Drug

Investigators must also assess the causal relationship of each AE to ACE-536. Factors for the assessment of causal relationship include, but are not limited to, temporal relationship between the AE and the administration of ACE-536, known side effects of ACE-536, medical history, concomitant therapy, course of the underlying disease and pertinent study procedures.

Probable: A causal relationship is clinically/biologically highly plausible and there is a plausible time sequence between onset of the AE and administration of ACE-536 and there is a reasonable response on withdrawal.

Possible: A causal relationship is clinically/biologically plausible and there is a plausible time sequence between onset of the AE and administration of ACE-536.

Unlikely: A causal relationship is improbable and another documented cause of the AE is most plausible.

Unrelated: A causal relationship can be definitively excluded and another documented cause of the AE is most plausible.

14.5. Documentation and Methods of Reporting of Adverse Events by Investigator

It is the responsibility of the Investigator to document all AEs that occur during the study. Patients will be evaluated and questioned generally for AEs during the course of the study, starting at the signing of the informed consent. The Investigator must report in detail all adverse signs and symptoms which are either volunteered by patients or observed during or following the course of investigational product administration on the appropriate CRF page. For patients

without treatment interruption, any AE ongoing at the time of EOT in A536-04 needs to be re-entered as an AE in A536-06. For patients with treatment interruption, all non-serious AEs occurring after signing of the ICF until a patient is dosed on C1D1 are to be documented on the medical history CRF. All AEs and SAEs occurring after the Cycle 1 Day 1 dose through 56 days after the last study drug administration (EOS visit) are to be reported and documented on the AE CRF.

All AEs spontaneously reported by the patient and/or in response to an open question from study personnel or revealed by observation, physical examination or other diagnostic procedures will be recorded on the AE CRF. Any clinically relevant changes in laboratory assessments, or other clinical findings as described in [Section 14.1](#), are considered AEs and must be recorded on the AE CRF. AEs are to be followed for resolution as described in Section 14.6.

It is important that each AE report include a description of the event, duration (onset and resolution dates), severity, relationship with ACE-536, any other potential causal factors, any treatment given or other action taken (including dose modification or discontinuation of ACE-536) and outcome. In addition, serious AEs (SAEs) should be identified and the appropriate seriousness criteria documented. AEs categorized as SAEs must also be documented using an SAE Report Form as described in Section 14.5.1.

Specific guidance can be found in the CRF Completion Guidelines provided by the Sponsor or designee.

14.5.1. Documentation of Serious Adverse Events

All SAEs that occur after the first study drug administration on Cycle 1 Day 1 until 56 days after the last study drug administration (EOS visit) are to be documented on the AE CRF. SAEs should not be reported for patients who are considered screen failures unless the event is deemed due to a protocol required procedure.

For all SAEs, an SAE form must be completed with as much information as possible and submitted within the time frame described in [Section 14.7](#).

When new significant information is obtained as well as when the outcome of an event is known, the investigator should record the information on a new SAE form. If the patient was hospitalized, a copy of the discharge summary must be included as part of the patient medical file. In all instances, the investigator should follow up with patients until the outcome of the SAE is known.

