7.3. Summary of Clinical Experience

The safety, tolerability, pharmacokinetics (PK), and pharmacodynamics (PD) effects of ACE-536 was evaluated in healthy postmenopausal women in a phase 1, randomized, double-blind, placebo controlled, multiple ascending dose study (Study A536-02). The primary objective of the study is to evaluate the safety and tolerability of ACE-536 in this population. Secondary objectives of the study are to examine the PK parameters and PD effects of ACE-536.

A total of 32 subjects were enrolled. Eligible subjects were healthy, postmenopausal women, 45-75 years old. The anticipated PD effect was an increase in plasma hemoglobin level. Screening and baseline hemoglobin values had to be between 11.0 and 14.5 g/dL, inclusive, to mitigate the risk of substantial excursions above the normal range. Sequential cohorts of 8 subjects each were randomized to receive either ACE-536 (n=6) or placebo (n=2) administered as a SC injection on Day 1 and Day 15. Each subject was to be followed for 112 days (16 weeks) after receiving their last dose of ACE-536 or placebo. The following dose levels were evaluated: 0.0625, 0.125, and 0.25 mg/kg.

ACE-536 administered every 2 weeks by subcutaneous (SC) injection for one or two doses at dose levels of 0.0625, 0.125 or 0.25 mg/kg was generally safe and well-tolerated in healthy postmenopausal female subjects. No serious or severe adverse events (AE) were reported. The majority of AEs were considered mild in severity. AEs that were considered at least possibly drug-related across ACE-536 dose groups included injection site hemorrhage (3 subjects), injection site macule (2 subjects), and dry skin, macule, hyperesthesia, muscle spasms, myalgia, generalized pruritus, and papular rash (1 subject each). Injection site pain was reported in one placebo-treated subject.

PK results indicated mean AUC and C_{max} values increased in a dose-proportional manner with ACE-536 dose level; mean T_{max} ranged from 7.0 to 9.8 days, and mean $T_{1/2}$ ranged from 14.9 to 16.2 days after the first dose. These PK results support intermittent SC dosing of ACE-536 in future studies, e.g., every 3 weeks.

PD assessments for hematological markers showed increases in hemoglobin levels at the 0.125 mg/kg dose level and more consistently at the 0.25 mg/kg dose level. Small increases in

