9.3.2. Inclusion Criteria

All patients must meet the following criteria:

1. Completion of the treatment period in the base study A536-04.
2. Females of child bearing potential (defined as sexually mature women who have not undergone hysterectomy or bilateral oophorectomy, or are not naturally postmenopausal ≥ 24 consecutive months) must have negative urine or blood pregnancy test prior to enrollment and use adequate birth control methods (abstinence, oral contraceptives, barrier method with spermicide, or surgical sterilization) during study participation and for 12 weeks following the last dose of ACE-536. Males must agree to use a latex condom during any sexual contact with females of child-bearing potential during study participation and for 12 weeks following the last dose of ACE-536, even if he has undergone a successful vasectomy. Patients must be counseled concerning measures to be used to prevent pregnancy and potential toxicities prior to the first dose of ACE-536.
3. Patient is able to adhere to the study visit schedule, understand and comply with all protocol requirements.
4. Patient understands and is able to provide written informed consent.

All patients with treatment interruption must also meet the following criteria:

Patients with treatment interruption (defined as patients who complete the EOS visit for study A536-04 and are ≥ 28 days post EOS visit) must also meet the following criteria:

5. Mean hemoglobin concentration < 10.0 g/dL of 2 measurements (not influenced by RBC transfusion) (one performed within one day prior to Cycle 1 Day 1 and the other performed during the screening period [Day -28 to Day -1]) in NTD patients.
6. Adequate folate levels or on folate therapy.
7. Platelet count $\geq 100 \times 10^9/L$ and $\leq 1,000 \times 10^9/L$.
8. Aspartate aminotransferase (AST) or alanine aminotransferase (ALT) $< 3 \times$ upper limit of normal (ULN).
9. Serum creatinine $\leq 1.5 \times$ ULN.
10. Ejection fraction $\geq 50\%$ by Echocardiogram (ECHO) or Multi gated acquisition scan (MUGA).

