5.8.1. Adverse Events

For patients with treatment interruption, all non-serious AEs occurring after signing of the ICF until a patient is dosed on C1D1 are to be documented on the medical history CRF. All AEs and SAEs occurring after the Cycle 1 Day 1 dose through 56 days after the last study drug administration are to be reported and documented on the AE CRF. All AEs collected in this study are treatment emergent adverse events (TEAE). A drug-related TEAE is defined as any TEAE related to the study medication as assessed by the investigator or with missing assessment of the causal relationship.

The following summaries will be presented for all dosed:

- Number and percentage of patients reporting each AE, categorized by System Organ Class (SOC) and Preferred Term (PT)
- Number and percentage of patients reporting each AE experienced by $\geq 5\%$ and $\geq 10\%$ of patients in all patients by PT
- Number and percentage of patients reporting SAE, categorized by SOC and PT
- Number and percentage of patients reporting Grade ≥ 3 AE, categorized by SOC and PT
- Number and percentage of patients reporting related AE, categorized by SOC and PT
- Number and percentage of patients reporting AE leading to drug withdrawal, categorized by SOC and PT
- Number and percentage of AE of interests by cycle

Note that counting will be by patient, not event, and patients are only counted once within each SOC or PT. If a patient experiences the same AE at more than one severity, or with more than one relationship to study drug, the most severe rating or the stronger causal relationship to study drug will be given precedence. Any missing severity, causality, or outcome will not be imputed and classed as unknown.

All AEs will be listed. The following listings will also be provided: 1) patients with SAEs; 2) patients with Grade ≥ 3 AEs; and 3) patients with AEs leading to study drug discontinuation; 4) death.

Concomitant medication use, severity, time to the worst CTCAE grade and recovery will be listed and summarized.

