5.8.6. Post-treatment Follow-up and Long-term Follow-up

A listing of post-treatment follow-up and Long-term follow-up data including the visit date, malignancy status, and survival status will be provided.

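### Apart from malignancy, an SAE judged drug related that starts more than 56 days after the last dose has no reporting route, and the texts on when capture ends disagree

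*Protocol*

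**What the plan says.** **The general window.** Protocol 14.5.1 sends to the AE page of the CRF "All SAEs that occur after the first study drug administration on Cycle 1 Day 1 until 56 days after the last study drug administration". Protocol 14.5 gives the same period and attaches a visit name to its end: "All AEs and SAEs occurring after the Cycle 1 Day 1 dose through 56 days after the last study drug administration (EOS visit". SAP 5.8.1 keeps the closing date without the visit name: "through 56 days after the last study drug administration are to be reported and documented on the AE CRF". Protocol 14.7 requires notice to the sponsor within 24 hours, but only for an SAE that falls inside the reporting period.

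**What runs longer.** Protocol 11.3 makes any new malignancy or premalignant lesion reportable as an SAE, whatever its cause, from consent through 3 years of follow-up. Protocol 14.1 sets 24-hour reporting for these events. SAP 5.8.6 promises a listing of follow-up data "including the visit date, malignancy status, and survival status will be provided". The long-term follow-up (LTFU) visits are described in the Schedule of Events as monitoring for malignancy and pre-malignancy.

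**Before the first dose.** Protocol 14.5 says "Patients will be evaluated and questioned generally for AEs during the course of the study, starting at the signing of the informed consent". For patients with treatment interruption it adds that "all non-serious AEs occurring after signing of the ICF until a patient is dosed on C1D1 are to be documented on the medical history CRF". Protocol 12.1 and footnote 3 of the Schedule of Events also place in medical history the medical events between the A536-04 End of Study (EOS) visit and Cycle 1 Day 1, with no limit on seriousness.

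**The concern.** The study exists to describe long-term safety. Suppose a patient has a serious, non-malignant event, such as a thromboembolic event, ten weeks after the last dose, and the investigator thinks the drug caused it. On the literal text it goes on no AE page, triggers no 24-hour notice and enters no table. If it is fatal, the death shows in the survival listing, but SAP 5.8.6 does not name its cause or relatedness among the listed items. A report with no late related SAEs could then mean that none occurred or that none were collected, and a reader could not tell which.

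The conflicting end dates add a second problem. Sites that work from different sections would collect different events, so late SAE counts would partly reflect which section a site followed.

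**Working it through.** The plan gives no figure to reproduce here. The check sets the texts side by side and then sizes the gap.

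**1. When does capture end?**

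| Source | End of AE or SAE capture, or timing of EOS |
|---|---|
| Protocol 14.5, 14.5.1 | 56 days after the last dose, labelled as the EOS visit |
| SAP 5.8.1 | 56 days after the last dose, no visit label |
| Protocol 14.6 | AEs recorded up to the end of the treatment period |
| Schedule of Events, AE row and footnote 24 | collected continuously; monitoring throughout the study |
| Protocol 12.6, Schedule footnote 28, SAP 5.1 | EOS about 3 years after the last dose |
| Protocol 9.4, SAP 3.2 | for early discontinuation, EOS about 28 days after the End of Treatment visit |

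These cannot all hold. In the base study, EOS was 56 days after the last dose (SAP Appendix 3, footnote 13), so the label may be carried over from there.

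**2. Is there a route after day 56?** Protocol 14.5.1 closes the AE page at day 56. Protocol 14.7 ties notification to the reporting period. Protocol 14.6 follows SAEs already recorded until they resolve or stabilise, but it does not open capture of new ones. The only stated extension is malignancy and premalignancy. None covers other related SAEs.

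**3. Share of follow-up covered.** Follow-up is 3 years: 3 × 365.25 = 1,095.75 days. Covered: 56 / 1,095.75 = 5.1%. Not covered: 1,095.75 − 56 = 1,039.75, about 1,040 days. Visits every 6 months over 36 months give 36 / 6 = 6 planned contacts, counting the one at 3 years.

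**4. Drug remaining at day 56.** Protocol 7.3 reports a mean half-life that "ranged from 14.9 to 16.2 days after the first dose", in healthy postmenopausal women. Assuming first-order decline, the fraction remaining is 0.5^(days / half-life):

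- half-life 14.9 days: 56 / 14.9 = 3.76 half-lives; 0.5^3.76 = 0.074
- half-life 16.2 days: 56 / 16.2 = 3.46 half-lives; 0.5^3.46 = 0.091

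So about 7% to 9% remains when the window closes.

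**5. The first visit after treatment ends.** The post-treatment visit is at 2 months ± 7 days. Taking 2 months as 61 days, it falls between day 54 and day 68, so up to 68 − 56 = 12 days after the window shuts. An event disclosed at that scheduled visit can already be outside the window.

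**The case against.** The best counter-argument is that this is a drafting conflict and not a decision to stop at day 56. If the EOS label is read with EOS at 3 years, and the schedule's continuous collection is followed, late SAEs are captured. That stands as a possible reading, but it cannot be relied on: 56 days is stated in both protocol sections and repeated in the SAP without the label, so it is the figure the analysis will use.

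A second argument is that most of the 1,040 uncovered days are free of drug. This also stands. The 5.1% describes coverage and does not measure missed related events. The half-life comes from phase 1 doses of 0.0625 to 0.25 mg/kg in healthy volunteers, not from these patients, and no document says that 7% to 9% residual drug makes a 56-day window inadequate.

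Three stronger readings are tempting and are not supported:

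- **All SAEs outside the window are lost.** Malignancy and premalignancy are reportable from consent through 3 years, and survival status is listed.
- **Serious events during screening go unrecorded.** Medical history in patients with treatment interruption takes pre-dose medical events of any seriousness. Patients without interruption have no screening procedures beyond consent, and AEs still ongoing at the A536-04 End of Treatment visit are re-entered. What remains unclear is only whether a serious pre-dose event in a patient who is later dosed needs an SAE form.
- **The protocol treats drug effect as lasting 12 weeks, so capture should run to day 84.** The 12 weeks is a contraception requirement ("during study participation and for 12 weeks following the last dose of ACE-536"). Nothing says that drug effect lasts that long. An 84-day limit would be a preference. It would still leave 1,095.75 − 84, about 1,012 days, outside general capture, and no visit is planned between about 2 months and month 6 to support it.

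**Conclusion.** The point holds in a limited form. Outside malignancy, premalignancy and survival status, a drug-related SAE that starts after day 56 has no stated route to the sponsor or to the tables, and the documents disagree on when capture ends. This rests on the literal 56-day text, which the SAP shares. The pharmacokinetic figure is supporting context only.

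The number of events affected cannot be estimated, because the documents give no rate of late related SAEs. It may be small. The case for acting is that the primary objective is long-term safety, the patients are already being seen, and without the change an absence of late related SAEs cannot be interpreted. This is an inexpensive improvement that should be made. It does not call the on-treatment safety tables into question.

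**What to change.** In Protocol 14.5, 14.5.1, 14.6 and 14.7 and SAP 5.8.1:

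1. State one window for all AEs and SAEs, ending 56 days after the last dose, and remove the EOS label from day 56. Bring the schedule's AE row and footnote 24 into line. Reconcile the EOS timing in Protocol 9.4 and SAP 3.2 with Protocol 12.6.
2. Add that any SAE the investigator considers related (possible or probable on the Protocol 14.4 scale) is recorded, and reported within 24 hours of awareness, at any time up to the 3-year EOS. Ask about it at the existing LTFU visits.
3. Show these late events in a separate post-treatment table. SAP 5.8.1 now calls every AE collected treatment emergent, so that sentence must exclude them. The 56-day tables then stay as they are.
4. For patients with treatment interruption, state that an SAE form is completed from consent onward and that pre-dose events stay out of the treatment-emergent tables. Medical history already records the event itself.

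The cost is wording in the protocol, the SAP and the CRF guidelines, plus one extra table. No visits or procedures are added. The downside is a few more SAE forms and slightly higher reported SAE counts. Some events will be learned of late: month 6 is about day 183, or 183 − 56 = 127 days after the general window closes.
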